4.0 Study Procedures

4.1 Subject Recruitment

It is planned at one site to enroll subjects into this trial. Therefore, based on the assumptions presented in Section 3.2, we will need to screen approximately 50 subjects to meet the target enrollment number of 30 subjects, and support a target completion number of 30. The target enrollment period for this study is 2 months.

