2.2 Study Design

2.2.1 General Study Design

This study is designed as a single cohort case series. After screening and enrollment, subjects will self-administer LITUS daily for 7 consecutive days.

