3.2 Anticipated Number of Research Subjects

Enrollment will be monitored at the assumed rates of Screen Failures and Discontinuation may be found to differ in this study from historical controls. The objective is to screen and enroll towards a target of 30 completed subjects.

Subjects to be Screened		50
Assumed Screen Fail Rate	30%	
Subjects to be Enrolled (sign ICF)		35
Assumed Discontinuation Rate	10%	
Total Number Completers (complete 24-wk treatment phase)		30

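### Section 4.1 sets enrolment at 30 with 30 completers, but the Section 3.2 assumptions it cites give 35 enrolled, and 30 enrolled would leave about 27 completers

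*Combined protocol and SAP*

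**What the plan says.** Section 3.2 (Anticipated Number of Research Subjects) sets out the recruitment chain in a small table: 50 screened, a 30% rate on the line "Assumed Screen Fail Rate", 35 enrolled (those who sign the consent form), a 10% rate on the line "Assumed Discontinuation Rate", and 30 completers. Its text adds: "The objective is to screen and enroll towards a target of 30 completed subjects". It also says: "Enrollment will be monitored at the assumed rates of Screen Failures and Discontinuation may be found to differ in this study from historical controls".

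Section 4.1 (Subject Recruitment) relies on that table: "based on the assumptions presented in Section 3.2, we will need to screen approximately 50 subjects". It then gives the purpose of the screening number as "to meet the target enrollment number of 30 subjects, and support a target completion number of 30".

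The completer line in Section 3.2 reads "Total Number Completers (complete 24-wk treatment phase", whereas Section 2.2.1 says that "subjects will self-administer LITUS daily for 7 consecutive days". Section 4.3.1 likewise describes a 1-week study, and the schedule in Section 4.6 puts the last visit at day 7.

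**The concern.** Section 4.1 names Section 3.2 as its source and then gives an enrolment number that Section 3.2 does not contain. The completion target appears to have been repeated as the enrolment target, which leaves no allowance for discontinuation.

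Thirty completers is the stated recruitment objective, and the plan has no power or precision calculation behind it. Section 4.1 is where a site would look for its recruitment target. A site that stopped enrolling at 30 would be expected to miss the completion target at the plan's own dropout rate.

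The 24-week label sits in the same table as the 10% rate, and the text above the table refers to historical controls. It is therefore unclear whether the 10% was set for a 1-week study.

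**Working it through.** **Inputs.** From Section 3.2: 50 screened, 30% screen failure, 35 enrolled, 10% discontinuation, 30 completers. From Section 4.1: about 50 screened, 30 enrolled, 30 completers.

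**Formulas.** Enrolled = screened × (1 − screen-fail rate). Completers = enrolled × (1 − discontinuation rate).

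**Section 3.2 reproduces.**
- Enrolled: 50 × 0.70 = 35, exactly as stated.
- Completers: 35 × 0.90 = 31.5, which covers the target of 30. Going from 35 to exactly 30 would be 1 − 30/35 = 14% discontinuation, so the table has a small margin.
- Backward: 30/0.90 = 33.3, so 34 enrolled; 34/0.70 = 48.6, so 49 screened. Both are close to the stated 35 and 50. The cruder inflation 30 × 1.10 = 33 does not give 30 either.

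**Section 4.1 does not reproduce.**
- Enrolled from 50 screened: 50 × 0.70 = 35, not 30. Taken as an exact yield, 30 of 50 implies 1 − 30/50 = 40% screen failure.
- Screening needed for 30 enrolled: 30/0.70 = 42.9, so 43, not about 50.
- Completers from 30 enrolled: 30 × 0.90 = 27, not 30. Thirty of 30 implies no discontinuation.

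**Chance of at least 30 completers.** Completers are taken as Binomial(enrolled, 1 − discontinuation rate), with independent dropouts. Only the 10% rate is in the documents; the lower rates are assumed, to cover the possibility that a 1-week study loses fewer subjects.

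| Discontinuation | Expected, 30 enrolled | P(30 complete), 30 enrolled | P(at least 30), 35 enrolled |
|---|---|---|---|
| 10% (plan) | 27.0 | 0.90^30 = 4% | 87% |
| 5% (assumed) | 28.5 | 0.95^30 = 21% | 99% |
| 3% (assumed) | 29.1 | 0.97^30 = 40% | above 99% |
| 2% (assumed) | 29.4 | 0.98^30 = 55% | above 99% |

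With 34 enrolled at 10%, the expected number is 34 × 0.90 = 30.6 and the probability is 75%.

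**Precision.** Confidence interval width scales with 1/√n, so 27 rather than 30 subjects gives √(30/27) = 1.054. With t quantiles the ratio is 1.059. The interval is about 5 to 6% wider.

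**The case against.** The strongest reply is that this is a copying slip with little consequence.

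- **Screening.** Fifty screened at 30% failure yields 35, which is enough to reach 30, so the implied 40% arises only if Section 4.1 is read as an exact yield. This has some force. However, Section 4.1 presents 50 as the number needed, and 43 would do for 30 enrolled. The discontinuation conflict does not depend on this reading.
- **No cap.** Nothing in the plan stops enrolment at 30. Section 3.2 enrols towards completers and monitors enrolment, so a site that follows it would probably recover. This stands and limits the harm.
- **Data from early stoppers.** Section 4.6 makes the second visit an early-termination visit as well, with WOMAC and diary collection, and Section 5 does not restrict the analysis to completers. Subjects who stop early may still contribute data, so the 5 to 6% is nearer an upper limit for the expected shortfall at the 10% rate. This stands.
- **The 10% rate.** The 4% figure uses a rate whose relevance to a 1-week study is itself in question, and it is simply the probability of no dropouts at all. That is fair, and it is why a range is shown. Even at 2%, 30 enrolled is little better than an even chance.
- **The 24-week label.** It is a separate matter of duration. It belongs here only because it sits in the table that supplies the dropout rate.

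None of these points makes 30 enrolled consistent with 30 expected completers at the plan's own 10% rate.

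**Conclusion.** The enrolment figure in Section 4.1 is wrong as written. Section 3.2 is coherent at 35, both sections agree on about 50 screened and 30 completers, and the figure out of line is the 30 enrolled in Section 4.1. If it were used as a stopping point, the expected shortfall would be three completers at 10% discontinuation. That result assumes independent dropouts, the plan's own rate, and enrolment actually ending at 30.

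The consequence is an ambiguous recruitment target and, at most, a modest loss of precision. No power statement is affected, because the plan makes none. It should be corrected, but it does not threaten the study.

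**What to change.** In Section 4.1, give 35 as the target enrolment, as Section 3.2 already does, and keep 30 as the completion target. In Section 3.2, reconcile the 24-week completer label with the 1-week study in Sections 2.2.1, 4.3.1 and 4.6, and confirm that the 10% discontinuation rate is meant for that study. If the rate changes, rework the table and carry the new enrolment figure into Section 4.1.

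The cost is a wording amendment. At the current rates it adds no subjects beyond the 50 screened and 35 enrolled already planned.

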4.1.1 Subject Compensation

Subjects will be compensated up to \$50 for participation in the study. Subjects will not be compensated for the initial screening/enrollment visit, but will \$50 for completed Visit 2.

4.2 Screening Procedures

Subjects will come to the clinic to be screened for inclusion in the study. The investigator or a sub-investigator will review the Eligibility Screening Checklist with the subject. All subjects must have physician-diagnosed mild to moderate knee OA (OARSI atlas grades 1-2).

4.3 Study Treatment

4.3.1 Treatment Groups

Subjects will participate in one treatment arm. All devices are manufactured by ZetrOZ Systems (Trumbull, CT) and are all identical. The 3 MHz device was FDA cleared in November 2013, and is marketed in the United States under the brand name sam[®]. All study subjects will apply 2 applicators affixed to the coupling bandages to their knee on the medial and lateral sides as shown in the figure below. The applicators are connected via a Y-adapter to a single power controller. The subjects will set the power controller to a 4-hour treatment duration for each daily treatment.

Sample Applicator Placement

This device delivers continuous ultrasound with a maximum acoustic power output of 1.3 W/cm² ±20% when 2 applicators are used. The frequency is 3 MHz ± 20%. The maximum treatment duration permitted is 4 hours per day.

Treatment protocol: subjects will self-administer the LITUS therapy for 4 hours per day at least 5 days (and up to 7 days) for the 1-week study.

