4.3.4 Treatment Adherence/ Study Compliance

Treatment compliance will be assessed by review of daily diaries and count of remaining bandages at the end of the study. The Research Coordinator will remind the subjects of the treatment protocol and retrain them on use of the device if necessary. Study visits should be completed within 3 days of the specified time in the Schedule of Assessments (Section 4.6).

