4.4 Follow-Up Procedures

4.4.1 Procedures to Assess Usability and Efficacy

Usability and Efficacy will be assessed at the end of the study. Subjects will maintain a Daily Diary at home, which will be a printed booklet that they will complete manually daily throughout the study period.

Daily Diary

Subjects will complete a Daily Diary throughout the 1-week treatment period to collect usability and pain ratings before, during and after treatment.

Numeric Rating Scale (NRS)

Subject-reported rating of pain severity, 0 = no pain, 10 = worst pain imaginable

Western Ontario and McMaster Universities Arthritis Index (WOMAC)

Subject reported rating of pain, stiffness and function validated for knee Osteoarthritis.

Exit Assessment

At the conclusion of the trial, each subject will be asked to complete an exit assessment form which solicits the subject's feedback on their use of the device, and satisfaction with therapy.

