4.6 Schedule of Assessments

Visit Number	V1	V1	V2			
Visit Type	Screening	Start Treatment	End of Treatment /Early Terminati on (3)			
Visit Day (1)	0	0	7			
Inclusion/Exclusion	×					
Criteria	^					
Informed Consent	x					
Medical history	x					
Treatment history	x					
Device Assignment Form		x				
Physical Examination	х					
Confirm baseline pain >4	×					
week preceding	^					
Train Subject on sam		x				
Device		^				
Confirm subject and put		x				
on and take off device						
WOMAC Scale		x	x			
Adverse Events		х	х			
Protocol Deviations			х			
Distribute Daily Diary		х				
Review/Collect Daily Diary			×			
Assess Compliance (2)			x			
Distribute sam Device		x				
with patches		X				
Distribute Patches		х				
Issue Subject						
Compensation and Signed			x			
Receipt						
Collect sam Device and			×			
Unused Patches			Α			
Exit Assessment			×			
Questionnaire			,			
1 Migit windows 12 days						

- 1 Visit window: ±3 days
- 2 Research coordinator should review subject diaries to ensure completeness, and evidence that subject is using the device per protocol.

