5.0 Data Management and Analysis

5.1 Outcome Measures and Data Analysis Plan

5.2 Change in NRS pain score from baseline will be analyzed for pre and post-treatment each treatment day throughout the study, and WOMAC (pain, stiffness, and functional change) will be evaluated on day 1 and day 7. Data will be analyzed using t-tests and repeated measure ANOVAs.

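### Compliant subjects may treat on 5, 6 or 7 days, but the planned repeated-measures ANOVA of daily NRS needs series of equal length; a mixed model would use every rating

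*Combined protocol and SAP*

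**What the plan says.** All references are to the combined protocol and SAP.

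- **Dosing rule.** Section 4.3.1 sets the treatment protocol at 4 hours per day, "at least 5 days (and up to 7 days) for the 1-week study". Section 2.2.1 puts it differently: "subjects will self-administer LITUS daily for 7 consecutive days".
- **Where the ratings come from.** Under section 4.4.1 subjects keep a paper diary "to collect usability and pain ratings before, during and after treatment".
- **What is analysed.** Section 5.2 states that change in NRS from baseline "will be analyzed for pre and post-treatment each treatment day throughout the study". WOMAC is evaluated on day 1 and day 7.
- **How.** "Data will be analyzed using t-tests and repeated measure ANOVAs". The section gives no analysis set, no rule for skipped days and no alternative model.
- **Visits.** Section 4.6 places Visit 2 on day 7, when the device and diary are collected, with the footnote "Visit window: ±3 days". Section 4.3.4 repeats the 3-day allowance.
- **Sample.** Section 3.2 targets 30 completers.

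**The concern.** Series of unequal length are built into the dosing rule here. They do not depend on dropout or poor compliance. A subject who treats on 5 days has met section 4.3.1 in full and has 5 pre/post pairs, while another compliant subject has 7.

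A standard repeated-measures ANOVA needs the same set of within-subject levels from everyone. The analyst then has two natural choices:

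- **Seven days as the factor.** Only subjects treated on all 7 days contribute.
- **Sessions 1 to 5 as the factor.** Every compliant subject contributes, but sessions 6 and 7 are set aside.

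These answer different questions. The first describes only people who never skipped, and the second describes only the early part of the course. Section 5.2 does not say which is meant, so the choice stays open until the data are seen. Pain reduction measured by NRS is a stated objective (section 2.1), and daily NRS is the only outcome with enough time points to call for this ANOVA.

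**Working it through.** **Inputs from the documents.** 5 to 7 treatment days (4.3.1); 30 completers (3.2); one pre/post pair per treatment day (4.4.1 and 5.2). The documents give no skip rate, SD or correlation.

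**1. The plan's own figures.** 50 × (1 − 0.30) = 35 enrolled, as stated. 35 × (1 − 0.10) = 31.5 against the stated 30, which is close enough. I use 30.

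**2. Pairs available.** Per subject, up to 2/7 = 28.6% of days may be absent with no deviation. For 30 completers who meet the minimum, the total lies between 30 × 5 = 150 and 30 × 7 = 210 pairs.

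**3. Pairs used by each form.** Let n7, n6 and n5 be the numbers treating on 7, 6 and 5 days, with n7 + n6 + n5 = 30 and total T = 7·n7 + 6·n6 + 5·n5.

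| Form | Pairs used | Share discarded, over all splits |
|---|---|---|
| 7 days | 7·n7 | 0% to 100% |
| First 5 sessions | 150 | 0% to 60/210 = 28.6% |
| Best of 5, 6 or 7 for each split | max(7·n7, 6·(n7 + n6), 150) | 0% to 23.5% |
| Mixed model | T | 0% |

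The worst split for the best fixed length is n7 = 21, n6 = 4, n5 = 5. Then T = 147 + 24 + 25 = 196, pairs used = max(147, 150, 150) = 150, and 46/196 = 23.5% are discarded. These are bounds, not expectations.

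**4. Illustration for the 7-day form (assumed skip rates).** Suppose each day is skipped independently with probability q, and keep only subjects with at least 5 days. The chance of a full series is (1 − q)^7 divided by the sum over k = 0, 1, 2 of C(7,k)·q^k·(1 − q)^(7−k).

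- q = 5%: 0.698/0.996 = 0.70, about 21 of 30 subjects.
- q = 10%: 0.478/0.974 = 0.49, about 15 of 30.
- q = 20%: 0.210/0.852 = 0.25, about 7 of 30.

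For the day-7 minus day-1 mean change (assumed SD 2, correlation 0.5), simulated standard errors for complete cases against a mixed model were 0.44 and 0.38 at q = 5%, 0.53 and 0.39 at 10%, and 0.79 and 0.40 at 20%.

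**5. Which mixed model.** A random subject intercept alone is not enough. It forces the same pre/post effect on every subject. Take m = 6 days, residual variance 1 and a subject-to-subject SD τ in the pre/post effect (all assumed), with no true mean effect.

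- True variance of a subject's mean difference: τ² + 2/m.
- Variance that the intercept-only model assigns: 2s²/m, where s² = 1 + (m·τ²/2)/(2m − 1).
- τ = 0.35: true 0.456; s² = 1.033, assigned 0.344; ratio 1.32, square root 1.15. The nominal 5% test uses 1.96/1.15 = 1.70, so it rejects about 9%.
- τ = 0.7: true 0.823; s² = 1.134, assigned 0.378; ratio 2.18, square root 1.48. It rejects about 18%.

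Simulations agree: about 9% at τ = 0.35 and 17% to 21% at τ = 0.7. A one-sample t-test on each subject's mean pre/post difference stayed near 5%. The model therefore needs a subject-level pre/post effect. It also needs a day-by-pre/post interaction, because section 5.2 asks for change on each treatment day.

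**The case against.** The strongest reply is that the loss is inferred, not planned. Section 5.2 does not say that incomplete subjects are dropped, and its unit is the treatment day, not a fixed 7-day calendar. That is correct. A reader might infer that the sponsor intends to exclude everyone who skipped a day, and the text does not support this. Exclusion is the likely result of a standard repeated-measures ANOVA, not a stated rule. What stands is that no rule is stated at all.

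A second reply is that this is a one-week case series with usability as an objective alongside pain, and no alpha, power or decision rule. This too is fair. The daily paired t-tests use every available pair, WOMAC is measured only twice, and usability does not depend on this model. It limits the importance of the point but does not remove it.

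A third reply cites the 7 consecutive days in section 2.2.1. Section 4.3.1 labels its own rule as the treatment protocol, and section 4.3.4 has the coordinator "remind the subjects of the treatment protocol and retrain them on use of the device if necessary", so a 5-day minimum is the natural reading. The difference is a matter of wording.

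A reader might also see the visit window as a second permitted source of short series. A Visit 2 on day 4 leaves 3 to 5 treatment days and on day 5 leaves 4 to 6, depending on whether day 0 and the visit day are treated. However, any series below 5 days breaks the section 4.3.1 minimum. With both rules applied the minimum stays at 5, so the window does not widen the range.

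**Conclusion.** The point holds as a low-cost improvement of modest weight. Compliant subjects can have daily NRS series of unequal length, and section 5.2 names a method that in its standard form cannot use them all.

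The discarded share is 0% if everyone treats on 7 days and at most 23.5% under the best fixed length. It can reach 100% for the 7-day form in the extreme case where nobody treats on all 7. The actual loss cannot be derived from the documents, and every figure based on a skip rate, SD or correlation above is an assumption.

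A reader might want one bound on the precision lost by using five sessions, and the documents do not support one. If all subjects treat on 7 days and their daily pre/post differences are uncorrelated, the standard error is √(7/5) = 1.18 times that from all data. Positive correlation between days makes it smaller, and the plan gives no correlation. The firmer argument is that the ANOVA's subjects and period are left undefined.

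**What to change.** In section 5.2, replace the repeated-measures ANOVA of daily NRS with a linear mixed model on all available treatment-day ratings:

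- fixed effects for treatment day, pre/post and their interaction;
- a random subject intercept and a random subject-level pre/post effect;
- if that model does not converge, a one-sample t-test on each subject's mean pre/post difference.

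Keep the paired t-tests, and report the number of treatment days per subject.

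**Cost.** A short text change and slightly more analysis work, with no added visits, subjects or data. The model assumes that skipped days are missing at random. This fails if subjects skip because of pain changes that their recorded ratings do not reflect. Reporting treatment days per subject helps readers judge that.

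**Optional wording.** Align section 2.2.1 with 4.3.1 (7 days intended, 5 the minimum). In section 4.6, say how an early in-window Visit 2 counts toward the 5-day minimum, or hold Visit 2 no earlier than day 6 except for early termination. The latter narrows the window and so has some cost for the site.

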4.3.2 Randomization

Not Applicable.

4.3.3 Breaking the Blind

Not Applicable

4.3.4 Treatment Adherence/ Study Compliance

Treatment compliance will be assessed by review of daily diaries and count of remaining bandages at the end of the study. The Research Coordinator will remind the subjects of the treatment protocol and retrain them on use of the device if necessary. Study visits should be completed within 3 days of the specified time in the Schedule of Assessments (Section 4.6).

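### The only post-baseline WOMAC is analysed as day 7, but the visit window lets it fall on Day 4 to Day 10 of a one-week treatment, part-way through the course or days after it

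*Combined protocol and SAP*

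**What the plan says.** All references are to the combined protocol and SAP.

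- **Visit timing.** The schedule in 4.6 puts screening and the start of treatment on Day 0 and V2 on Day 7. Footnote 1 there reads "Visit window: ±3 days". Section 4.3.4 says the same in words: "Study visits should be completed within 3 days of the specified time in the Schedule of Assessments (Section 4.6").
- **WOMAC.** The schedule marks it twice only, in the "Start Treatment" column and at V2. Section 5 evaluates it on day 1 and day 7, using t-tests and repeated-measures ANOVA.
- **What else happens at V2.** The schedule rows beginning "Collect sam Device and" and "Review/Collect Daily Diary" are both marked there. V2 also serves as the early-termination visit.
- **Length of treatment.** Section 2.2.1: "subjects will self-administer LITUS daily for 7 consecutive days". Section 4.3.1: "at least 5 days (and up to 7 days) for the 1-week study".
- **Compliance.** Section 4.3.4: "Treatment compliance will be assessed by review of daily diaries and count of remaining bandages at the end of the study".

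**The concern.** A window of three days either side is wide when the whole treatment lasts one week. Nothing ties the V2 WOMAC to the last session. Section 5 sets no analysis window and makes no use of the actual visit day or the number of sessions received. One WOMAC per subject carries the whole post-baseline result on that instrument, which is one of the two named in the efficacy objective (2.1). With a single cohort, no control group shares the same variation in timing.

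There is also a conflict between the sections. Because the device goes back at V2, an early visit ends treatment. A site can keep to the visit window and still make the treatment schedule in 2.2.1, or even the minimum in 4.3.1, impossible to meet.

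**Working it through.** The plan states no figure for this, so there is none to reproduce. The check is a direct count.

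**Inputs.** V2 is nominally Day 7, window 3 days either side (4.6, 4.3.4). The full course is seven daily sessions (2.2.1) and the permitted range is 5 to 7 (4.3.1). The first session is on Day *s*. The schedule points to *s* = 0. Section 5 calls the first WOMAC day 1, so *s* = 1 is shown as the alternative.

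**Window.** 7 − 3 = 4 and 7 + 3 = 10, so V2 is on Day *d* = 4 to 10, seven possible days.

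**Formulas, no session missed.** Sessions fall on Days *s* to *s* + 6.

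- Sessions before V2 = min(7, *d* − *s*).
- Counting a session on the visit day before the WOMAC = min(7, *d* − *s* + 1).
- Days since the last session, with no visit-day session = *d* − min(*s* + 6, *d* − 1).

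| V2 day | Day-0 start: sessions (with visit-day session) | Day-0 start: days since last | Day-1 start: sessions (with visit-day session) | Day-1 start: days since last |
|---|---|---|---|---|
| 4 | 4 (5) | 1 | 3 (4) | 1 |
| 5 | 5 (6) | 1 | 4 (5) | 1 |
| 6 | 6 (7) | 1 | 5 (6) | 1 |
| 7 | 7 (7) | 1 | 6 (7) | 1 |
| 8 | 7 (7) | 2 | 7 (7) | 1 |
| 9 | 7 (7) | 3 | 7 (7) | 2 |
| 10 | 7 (7) | 4 | 7 (7) | 3 |

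**Five early sessions, which 4.3.1 allows.** The last session is on Day 4 (Day-0 start) or Day 5 (Day-1 start). A Day-10 WOMAC then comes 10 − 4 = 6 or 10 − 5 = 5 days later.

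**Against the treatment schedule.**

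- A visit on Day 4 or Day 5 allows at most 6 sessions under either start, even with a visit-day session. Seven days in a row is then impossible.
- A Day-4 visit gives 4 sessions on a Day-0 start, below the minimum of five unless a session is done that day before V2. On a Day-1 start it gives 3 or 4, below the minimum either way.

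**Effect of a Day 7 to Day 8 window, as an example.** The largest gap for subjects with 5 to 7 sessions falls from 6 to 8 − 4 = 4 days (Day-0 start), or from 5 to 8 − 5 = 3 days (Day-1 start). With no session missed, a Day-0 start gives 7 sessions on both days. A Day-1 start still mixes 6 and 7 unless a session is done on Day 7 before the visit.

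**The case against.** The best defence has four parts.

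1. **Start day.** The schedule labels Day 0 as the start of treatment and places training and device distribution there. The day 1 in Section 5 may only be another numbering of the same visit. This stands: Day 0 is the better-supported reading, and the lowest counts (3 sessions) belong to the weaker one.
2. **Early visits are unlikely.** V2 is labelled as the end of treatment, so a site would have little reason to book it on Day 4, and compliance and protocol deviations are recorded there. This stands in part. The early side is mainly a conflict between sections, and nothing shows that early visits are expected. The late side needs no such conflict: a Day-10 visit agrees with every stated rule.
3. **Small stakes.** This is a case series aiming for 30 completers, with usability listed as the first objective, and the daily NRS already shows the course of pain. This limits the weight of the point. But the NRS rates pain only, so stiffness rests on the WOMAC, and the diary is also collected at V2.
4. **A footnote is not visible.** The V2 column carries a marker (3) whose text does not appear in the copy reviewed. It may bear on this visit, and its content is unknown.

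A reader might also infer that off-time visits would dilute the change and so understate the benefit. The documents do not support this. They do not say how WOMAC moves with sessions or after the last one. The cohort is selected on pain in the preceding week (3.3), so scores may drift with time whatever the device does. Nor do the seven possible days translate into shares of subjects: they are calendar days, not probabilities.

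**Conclusion.** The point holds and should be acted on, with moderate confidence. What Section 5 treats as a day-7 WOMAC can, within the rules, be a part-course, end-of-course or post-course value. On the Day-0 reading with no session missed, it follows 4 to 7 sessions (5 to 7 with a visit-day session) and comes up to 4 days after the last, or up to 6 days with five early sessions. On the Day-1 reading it follows 3 to 7 sessions (4 to 7) and comes up to 3 days after, or up to 5.

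These figures rest on the stated window, daily sessions and the assumed start day. They describe what the plan permits. They do not show that the WOMAC result will be materially distorted: the size and direction of any effect, and how often visits will run off time, cannot be computed from the documents.

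**What to change.** 1. **Sections 4.3.4 and 4.6.** Remove the early side of the window for the scheduled V2 WOMAC and shorten the late side, for example to Day 7 to Day 8. Set the exact days once the first-session day is stated, so that the planned course can be finished before the assessment. Flag early-termination WOMACs separately, since they share V2 and may fall on any day. Cost: less scheduling flexibility. The narrower window only partly helps subjects with 5 or 6 sessions, whose last session may still be some days back.
2. **Section 5.** Report the actual V2 day, sessions done and days since the last session. Add a sensitivity analysis limited to WOMACs inside the narrowed window. Cost: a little more analysis and no new data, since visit dates and diaries are already collected. The sensitivity analysis will have fewer than the 30 planned completers if visits run off time.
3. **Reconciliation by the sponsor.** Bring into agreement the seven-day course in 2.2.1, the 5-to-7-day range in 4.3.1, the visit window, and Day 0 in 4.6 against day 1 in Section 5, and state the day of the first session. Which treatment rule applies is for the sponsor to settle. Cost: wording only.
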